## FLOW CHART - IV GROUP

Period	Visit	Day	Planned time (relative to first drug administration) [h:min]	Approximate clock time of actual day [h:min]	Event and comment	Safety laboratory	PK serum	12-lead ECG	Vital signs (BP, PR)	Questioning for AEs and concomitant therapy 	Query regarding local tolerability 
SCR	1	-21 to -3			Screening (SCR) 	x		x	x		
	2	-2	-48:00	8:00	Ambulatory visit	x 				x	
		-1	-14:00	18:00	Admission to trial site	x 				x	
		1	-3:00	06:00	Allocation to treatment 	x 	x 	x 	x 	x 	
			0:00	08:00	Drug administration start of infusion						
			0:30	08:30	end of infusion		x	x		x	x
			2:00	10:00	Light breakfast 		x	x	x		x
			4:00	12:00			x	x	x	x	
			8:00	16:00	Snack (voluntary) 		x	x	x		
			12:00	20:00			x	x	x	x	x
			24:00	08:00	Breakfast 	x	x	x	x	x	
			34:00	18:00	Dinner 		x		x	x	
			48:00	08:00	Breakfast  , discharge from trial site (confirmation of fitness) 		x	x	x	x	
		4	72:00	08:00	Ambulatory visit		x				x
		6	120:00	08:00	Ambulatory visit		x				x
		8	168:00	08:00	Ambulatory visit	x	x	x	x	x	
		11	240:00	08:00	Ambulatory visit		x				x
		14	312:00	08:00	Ambulatory visit	x	x	x	x	x	
		21	480:00	08:00	Ambulatory visit		x	x	x	x	
		28	648:00	08:00	Ambulatory visit	x	x	x	x	x	
		56	1320:00	08:00	Ambulatory visit	x	x	x	x	x	
FU	3	56 to 59			End of trial (EoTrial) examination 	x		x	x	x	x

1. Subject must be informed and written informed consent obtained prior to starting any screening procedures. Screening procedures include physical examination, check of vital signs, inclusive body temperature if it is still needed based on the status of pandemic, ECG, safety laboratory (including drug screening), demographics (including determination of body height and weight, smoking status and alcohol history), relevant medical history, concomitant therapy and review of inclusion/exclusion criteria.
2. The time is approximate; the procedure is to be performed and completed within the 3 h prior to drug administration.
3. If several actions are indicated at the same time, the intake of meals will be the last action.
4. At the end of trial visit the EoTrial examination includes physical examination, vital signs, ECG, safety laboratory, recording of AEs and concomitant therapies. EOT to be performed not before last PK sampling.

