## FLOW CHART - SC GROUP

Period	Visit	Day	Planned time (relative to first drug administration) [h:min]	Approximate clock time of actual day [h:min]	Event and comment	Safety laboratory	PK serum	12-lead ECG	Vital signs (BP, PR)	Questioning for AEs and concomitant therapy 	Query regarding local tolerability 
SCR	1	-21 to -3			Screening (SCR) 	x		x	x		
	2	-2	-48:00	8:00	Ambulatory visit	x 			x	x	
		-1	-14:00	18:00	Admission to trial site	x 				x	
		1	-3:00	06:00	Allocation to treatment 	x 	x 	x 	x 	x 	
			0:00	08:00	Drug administration/injection						x
			0:30	08:30						x	x
			1:00	09:00					x	x	
			1:30	09:30					x	x	
			2:00	10:00	Light breakfast 			x	x	x	
			3:00	11:00				x	x	x	
			4:00	12:00			x	x	x	x	x
			8:00	16:00	Snack (voluntary) 			x	x	x	
			12:00	20:00			x	x	x	x	x
		2	24:00	08:00	Breakfast 	x	x	x	x	x	x
			3	48:00	08:00		x	x	x	x	x
		4	72:00	08:00	Breakfast  , discharge from trial site (confirmation of fitness  )	x		x	x	x	x
			5	96:00	08:00	Ambulatory visit		x		x	x
			6	120:00	08:00	Ambulatory visit		x		x	x
			7	144:00	08:00	Ambulatory visit	x	x	x	x	x
			8	168:00	08:00	Ambulatory visit		x		x	
			11	240:00	08:00	Ambulatory visit		x		x	
			14	312:00	08:00	Ambulatory visit	x	x	x	x	
			21	480:00	08:00	Ambulatory visit		x	x	x	
			28	648:00	08:00	Ambulatory visit	x	x	x	x	
			56	1320:00	08:00	Ambulatory visit	x	x	x	x	
FU	3	56 to 59			End of trial (EoTrial) examination 	x		x	x	x	

1. Subject must be informed and written informed consent obtained prior to starting any screening procedures. Screening procedures include physical examination, check of vital signs, inclusive body temperature if it is still needed based on the status of pandemic, ECG, safety laboratory (including drug screening), demographics (including determination of body height and weight, smoking status and alcohol history), relevant medical history, concomitant therapy and review of inclusion/exclusion criteria.
2. The time is approximate; the procedure is to be performed and completed within the 3 h prior to drug administration.
3. If several actions are indicated at the same time, the intake of meals will be the last action.

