#### 7.3.4 Safety analyses

Safety will be analysed based on the assessments described in Section [2.2.2.2](#) and [2.2.2.3](#). All treated subjects (TS, refer to Section [7.2](#)) will be included in the safety analysis. Safety analyses will be descriptive in nature and based on BI standards. No hypothesis testing is planned.

For all analyses, the treatment actually administered (= treatment at onset) to the subject will be used (any deviations from the treatment will be discussed in the minutes of the Report Planning Meeting).

Treatments will be compared in a descriptive way. Tabulations of frequencies/proportions will be used to evaluate categorical (qualitative) data, and tabulations of descriptive statistics will be used to analyse continuous (quantitative) data.

Measurements (such as ECG, vital signs, or laboratory parameters) or AEs will be assigned to treatments (see Section [4.1](#)) based on the actual treatment at the planned time of the measurement or on the recorded time of AE onset (concept of treatment emergent AEs). Therefore, measurements planned or AEs recorded prior to first intake of trial medication will be assigned to the screening period, those between first trial medication intake and end of trial examination (including the anticipated REP (see Section [1.2.3](#))) will be assigned to the treatment period. These assignments including the corresponding time intervals will be defined in detail in the TSAP. Note that AEs occurring after the last per protocol contact but entered before final database lock will be reported to Pharmacovigilance only and will not be captured in the trial database.

Adverse events will be coded using the Medical Dictionary for Regulatory Activities (MedDRA). Frequency, severity, and causal relationship of AEs will be tabulated by treatment, system organ class, and preferred term. SAEs, AESIs (see Section [5.2.6.1](#)), and other significant AEs (according to ICH E3) will be listed separately.

Previous and concomitant therapies will be presented per treatment group without consideration of time intervals and treatment periods.

Laboratory data will be compared to their reference ranges. Values outside the reference range as well as values defined as possibly clinically significant will be highlighted in the listings. Additionally, differences from baseline will be evaluated.

Vital signs or other safety-relevant data will be assessed with regard to possible on-treatment changes from baseline.

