6. GENERAL ANALYSIS DEFINITIONS

6.1 TREATMENTS

For basic study information on treatments to be administered, assignment of treatment groups, and selection of doses, cf. Section 4 of the CTP.

Subjects will receive 100 mg BI 765080 either as

- subcutaneous injection as bolus (Test Treatment T)

or as

- 30 minute intravenous infusion (Reference Treatment R)

For statistical analysis of AEs, the following analysis phases are defined for each subject.

Table 6.1: 1 Analysis phases for statistical analysis of AEs, and actual treatment for analysis of laboratory data and vital signs

Study analysis phase	Label	Start	End
Screening ¹	Screening	Date of informed consent	Date/time of start of administration of study drug
On-treatment	BI SC or BI IV	Date/time of start of administration of study drug	12:00 a.m. on day after last contact date

¹ See [Section 6.7](#) for definition of baseline, which will be used in the statistical analyses of safety laboratory data, ECG and vital signs.

AE summary tables will present results for the on-treatment phase only. All AEs will be listed.

In AE tables in CTR Section 15.3 (but not in Appendix 16.1.13.1.8.1), the following total will be provided in addition:

- "Total", defined as the total over on-treatment phases BI injection and BI infusion

Safety laboratory data, vital signs and PK [REDACTED] parameters will be analysed based on treatment groups with clear differentiation between baseline (cf. [Section 6.7](#)) and on-treatment measurements. Measurements will be considered on-treatment, if they were taken within the on-treatment phases as defined in Table 6.1: 1.

More details on the technical implementation of these analyses are provided in the ADS Plan of this TSAP.

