7.8.2 Laboratory data

The analyses of laboratory data will be descriptive in nature and will be based on BI standards “Display and Analysis of Laboratory Data” ([9](#)).

Analyses will be based on normalised values, which means transforming to a standard unit and a standard reference range. The original values will be analysed if the transformation into standard unit is not possible for a parameter.

Descriptive statistics of laboratory values over time and for the difference from baseline (see [Section 6.7](#)) will be provided. Frequency tables of changes between baseline and last value on treatment with respect to the reference range will be presented.

Unscheduled measurements of laboratory data will be assumed to be repeat measurements of the most recent scheduled measurement (e.g. for follow-up or confirmation of a particular value). Therefore, unscheduled measurements will be assigned to the planned time point of the previous scheduled measurement. Descriptive statistics will be calculated by planned time point based on the worst value of the subject at that planned time point (or assigned to that planned time point).

Clinically significant abnormal laboratory values are only those identified either in the Investigator's comments or at the Report Planning Meeting at the latest. It is the Investigator's responsibility to decide whether a lab value is clinically significant abnormal or not.

Laboratory data will be compared to their reference ranges. Values outside the reference range as well as possibly clinically significant values will be highlighted in the listings. Possibly clinically significant laboratory values will be listed in Section 15.4.1.

Clinically relevant findings in laboratory data will be reported as baseline conditions (prior to start of administration of study treatment) or as AEs (after start of administration of study treatment) if judged clinically relevant by the investigator, and will be analyzed as such.

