7.8.3 Vital signs

The analyses of vital signs (blood pressure, pulse rate) will be descriptive in nature. Descriptive statistics of vital signs over time and for the difference from baseline (see [Section 6.7](#)) will be provided.

Unscheduled measurements of vital signs will be assigned to planned time points in the same way as described above for laboratory data (i.e., they will be assigned to the previous planned time point).

Descriptive statistics will be calculated by planned time point based on the last value of the subject at that planned time point (or assigned to that planned time point). This is based on the assumption, that the last value is a repeat measurement due to quality reasons and is therefore more reliable than the first measurement. The assumption of a repeat measurement due to quality reasons is only plausible if the unscheduled measurement is shortly after the scheduled measurement. In order to assess the time difference (during data validation and Report Planning Meeting), the date and clock time of both measurements has to be available. If the time of measurement is missing for a scheduled or unscheduled post-baseline measurement (or both), the scheduled measurement will be used in calculation of descriptive statistics (since it cannot be assessed whether the assumption of a repeat measurement for quality reasons is plausible, or not). All measurements will be listed.

Clinically relevant findings in vital signs data will be reported as baseline conditions (prior to start of administration of study treatment) or as AEs (after start of administration of study treatment) if judged clinically relevant by the investigator, and will be analyzed as such.

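### The SAP's previous-slot rule does not stop at dosing, so an unscheduled laboratory value from the first 24 h after dosing is tabulated in the pre-dose row

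*SAP*

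**What the plan says.** **Laboratory data (SAP 7.8.2).** The premise is that "Unscheduled measurements of laboratory data will be assumed to be repeat measurements of the most recent scheduled measurement". It follows in the SAP that "unscheduled measurements will be assigned to the planned time point of the previous scheduled measurement". The by-time-point statistics are then "based on the worst value of the subject at that planned time point (or assigned to that planned time point". The section has no time limit, no timing check and no exception for dosing.

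**Vital signs (SAP 7.8.3).** Unscheduled values are handled in the same way: "they will be assigned to the previous planned time point". Here the last value is summarised, not the worst. The section accepts that a quality repeat is plausible only soon after the scheduled reading, and has the time difference looked at during data validation and the Report Planning Meeting. If a clock time is missing, the scheduled value is used. It does not define how soon is soon enough, and does not say where a value judged not to be a repeat should go.

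**Phase and baseline (SAP 6.1 and 6.7).** SAP 6.1 asks for a clear split between baseline and on-treatment data: "Measurements will be considered on-treatment, if they were taken within the on-treatment phases". Table 6.1: 1 starts that phase at the date and time when administration begins. SAP 6.7 takes baseline as the last value before the infusion or injection starts.

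**The concern.** A value taken after dosing can carry two incompatible labels. By SAP 6.1 it is on-treatment. By SAP 7.8.2 its row in the table is pre-dose. For laboratory data the worst-value rule makes this more than a label: an abnormal post-dose result displaces the genuine pre-dose result in that row, while the first post-dose row does not show it.

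Unscheduled blood tests are foreseen. The protocol's section on adverse events of special interest calls for one, if needed, when hepatic symptoms appear without laboratory results, and its laboratory section allows retests. At stake is whether the by-time-point tables for the IV and SC groups show an early post-dose change on the correct side of the dose.

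**Working it through.** **Inputs.** Slots come from the two protocol flow charts, in hours relative to dosing.

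| | Last pre-dose slot | First post-dose slot, IV | First post-dose slot, SC |
|---|---|---|---|
| Safety laboratory | Day 1, -3:00 | 24:00 | 24:00 |
| Vital signs | Day 1, -3:00 | 2:00 | 1:00 |

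The pre-dose procedures are to be completed within the 3 h before dosing. The charts were read from PDF and some cells in the SC chart are displaced, so the 1:00 and 2:00 vital-sign slots are less certain than the laboratory slots.

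**Step 1: apply the rule.** Assigned slot = latest scheduled slot at or before the time of the unscheduled value.

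- Laboratory sample at 3 h: the latest slot not after 3 h is -3:00, so it is filed as pre-dose. The same holds for any time from 0 to just under 24 h, in both arms.
- Vital signs at 0.5 h: the latest slot is again -3:00 in both arms, so they are filed as pre-dose unless the timing review intervenes.

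**Step 2: which value fills the row.** For laboratory data it is the worse of the scheduled pre-dose value and the unscheduled post-dose value. For vital signs it is the later one, which is the post-dose reading.

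**Step 3: compare with SAP 6.1 and 6.7.** The sample at 3 h was taken after the start of administration, so SAP 6.1 makes it on-treatment and SAP 6.7 bars it from being baseline. Only the row label in the by-time-point table is wrong.

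**Step 4: size.** The protocol plans 14 subjects per arm. One value that differs by d from the one it displaces moves the row mean by d/14. The following values are assumed, chosen only to show the arithmetic:

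- Laboratory: 200 in place of 25 U/L gives (200 - 25)/14 = +12.5 U/L in the pre-dose row, and no change in the 24:00 row.
- Systolic pressure: 85 in place of 120 mmHg gives (85 - 120)/14 = -2.5 mmHg in the pre-dose row, if the timing review lets the value through.

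**Step 5: late values.** Days 29 to 55 run from 664 h to 1312 h, between the slots at 648 h (Day 28) and 1320 h (Day 56). A value in that span is labelled Day 28. The gap between slots is (1320 - 648)/24 = 28 days. Both slots are after dosing, so no boundary between phases is crossed.

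**The case against.** The strongest case against is that little of consequence depends on this row.

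- **Baseline and phase.** A reader might infer that post-dose values are lost from the on-treatment data or contaminate baseline. The documents do not support that: SAP 6.1 and 6.7 both go by actual time, and the shift tables use baseline and the last on-treatment value. This objection stands and limits the point to the by-time-point tables.
- **Protocol 7.3.4.** Its wording that "measurements planned or AEs recorded prior to first intake of trial medication will be assigned to the screening period" might suggest that such a value would be sent to the screening period. But an unscheduled value has no planned time of its own, and the same section leaves the detailed intervals to the SAP. A conflict with the protocol is an inference and is not claimed.
- **Days 29 to 55.** Labelling these values Day 28 might look like misclassification. It is a coarse label within the on-treatment phase and the same in both arms.
- **Vital signs.** A reading during the infusion is the kind of case the timing review can catch. That stands in part: the review has no cut-off and no alternative slot.
- **Other safeguards.** Individual values are listed, possibly clinically significant laboratory values are listed separately, and clinically relevant findings after dosing become adverse events.
- **Documents not available.** The ADS Plan and the sponsor's laboratory standard might contain an exception. Neither can be checked, and nothing in the SAP says that they override its explicit rule.

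None of this answers the laboratory case: followed as written, SAP 7.8.2 puts a post-dose result in a pre-dose row.

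**Conclusion.** The point holds for the by-time-point safety tables. It is clearest for laboratory data, where the window is the first 24 h after dosing in both arms, no timing check exists and the worst-value rule can displace the true pre-dose value. For vital signs it holds in weaker form, for the first 2 h (IV) or 1 h (SC) as the charts read, because the timing review may catch the value but has nowhere to put it.

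The size is one fourteenth of the displaced difference per affected value. The documents give no expected number of unscheduled samples, and nothing in them shows that such samples are mostly prompted by adverse reactions, so the total effect cannot be estimated and may be nil. The tables are descriptive, and neither the PK endpoints nor the drug-related adverse-event endpoint changes. The conclusion assumes that the SAP rule is programmed as written.

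**What to change.** Add to SAP 7.8.2 and 7.8.3 that an unscheduled value taken after the start of administration is never assigned to a pre-dose time point. If it precedes the first scheduled post-dose slot, assign it to that slot. State that on-treatment status follows actual time, as in SAP 6.1.

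Under this change an early laboratory value competes with the 24:00 value under the worst-value rule, which is still coarse but on the correct side of the dose. For vital signs the scheduled reading at the first post-dose slot would normally be the last one and so be summarised, with the early reading in the listings.

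Keep the previous-slot rule for all other post-dose values. Nearest-slot assignment is not needed and has its own cost: in the IV arm, a Day 12 confirmation of a Day 8 result (264 h, against slots at 168 h and 312 h) would move to Day 14. A maximum distance, or a worst-on-treatment summary that the SAP does not plan, is also unnecessary for this point.

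The cost is one clause in each of two sections and a small change to the time-point derivation, with no change to data collection.

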7.8.3 Vital signs

The analyses of vital signs (blood pressure, pulse rate) will be descriptive in nature. Descriptive statistics of vital signs over time and for the difference from baseline (see [Section 6.7](#)) will be provided.

Unscheduled measurements of vital signs will be assigned to planned time points in the same way as described above for laboratory data (i.e., they will be assigned to the previous planned time point).

Descriptive statistics will be calculated by planned time point based on the last value of the subject at that planned time point (or assigned to that planned time point). This is based on the assumption, that the last value is a repeat measurement due to quality reasons and is therefore more reliable than the first measurement. The assumption of a repeat measurement due to quality reasons is only plausible if the unscheduled measurement is shortly after the scheduled measurement. In order to assess the time difference (during data validation and Report Planning Meeting), the date and clock time of both measurements has to be available. If the time of measurement is missing for a scheduled or unscheduled post-baseline measurement (or both), the scheduled measurement will be used in calculation of descriptive statistics (since it cannot be assessed whether the assumption of a repeat measurement for quality reasons is plausible, or not). All measurements will be listed.

Clinically relevant findings in vital signs data will be reported as baseline conditions (prior to start of administration of study treatment) or as AEs (after start of administration of study treatment) if judged clinically relevant by the investigator, and will be analyzed as such.

7.8.4 ECG

Abnormal findings will be reported as baseline conditions (at screening) or as AEs (during the trial) if judged clinically relevant by the investigator and will be analyzed as such. No separate listing or analysis of ECG data will be prepared.

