Proprietary confidential information © 2021 Boehringer Ingelheim International GmbH or one or more of its affiliated companies

QT	Time between start of the Q-wave and the end of the T-wave in an electrocardiogram
QTc	QT interval corrected for heart rate using the method of Fridericia (QTcF) or Bazett (QTcB)
R	Reference treatment
REP	Residual effect period
SAE	Serious adverse event
SARS-CoV-2	Severe acute respiratory syndrome coronavirus 2
SC/s.c.	subcutaneous
SCR	Screening
SGLT2	Sodium-glucose co-transporter-2
SNP	Single nucleotide polymorphism
SOP	Standard operating procedure
SRD	Single-rising dose
T	Test product or treatment
Tie2	Angiopoietin-1 receptor, TEK tyrosine kinase
TMDD	Target mediated drug disposition
TMF	Trial master file
$t_{1/2}$	Terminal half-life of the analyte in plasma
$t_{\text{max}}$	Time from (last) dosing to the maximum measured concentration of the analyte in plasma
TS	Treated set
TSAP	Trial statistical analysis plan
ULN	Upper limit of normal
WBC	White blood cells
WFI	Water for Injection
WHO	World Health Organisation
WOCBP	Women of child-bearing potential
XTC	Ecstasy

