#### **3.3.4.3 Discontinuation of the trial by the sponsor**

Boehringer Ingelheim reserves the right to discontinue the trial at any time for any of the following reasons (if reasons 4 and/or 5 are met, the trial should be discontinued immediately):

1. Failure to meet expected enrolment goals overall or at a particular trial site
2. The sponsor decides to discontinue the further development of the investigational product
3. Deviation from GCP, or the CTP, or the contract with BI impairing the appropriate conduct of the trial.
4. New toxicological findings, serious adverse events, or any safety information invalidating the earlier positive benefit-risk-assessment.
5. More specifically, the trial will be terminated if more than 50% of the subjects have drug-related and clinically relevant adverse events of moderate or severe intensity, or if at least 1 drug-related serious adverse event is reported
6. Further dosing will be stopped if at least 2 subjects at one group (14 subjects) have relevant individual QT prolongations, i.e. a QTc increase of greater than 60 ms from baseline in connection with absolute QT or QTc greater than 500 ms, as confirmed by a repeat ECG recording
7. Occurrence of severe non-serious adverse events considered as drug-related by the investigator in 2 subjects of one group (14 subjects)

The investigator / trial site will be reimbursed for reasonable expenses incurred in case of trial termination (except if item 3 applies).

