#### 5.2.4      **Electrocardiogram**

Twelve-lead ECGs (I, II, III, aVR, aVL, aVF, V1 - V6) will be recorded using a computerised electrocardiograph ([REDACTED]) at the times provided in the [Flow Chart](#).

To achieve a stable heart rate at rest and to assure high quality recordings, the site personnel will be instructed to assure a relaxed and quiet environment, so that all subjects are at complete rest.

All ECGs will be recorded for approximately 10 sec duration after subjects have rested for at least 5 min in a supine position. ECG assessment will always precede all other study procedures scheduled for the same time to avoid compromising ECG quality.

All ECGs will be recorded, interpreted and stored electronically at the site. Electrode placement will be performed according to the method of Wilson, Goldberger and Einthoven modified by Mason and Likar (hips and shoulders instead of ankles and wrists).

All locally printed ECGs will be evaluated by the investigator or a designee. Abnormal findings will be reported as AEs (during the trial) or baseline conditions (at screening) if assessed to be clinically relevant by the investigator. Any ECG abnormalities will be carefully monitored and, if necessary, the subject will be removed from the trial and will receive the appropriate medical treatment.

ECGs may be repeated for quality reasons (for instance, due to alternating current artefacts, muscle movements, or electrode dislocation) and the repeated ECG will be used for analysis. Additional (unscheduled) ECGs may be collected by the investigator for safety reasons.

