7. PLANNED ANALYSIS

The format of the listings and tables will follow the BI guideline "Reporting of clinical trials and project summaries" (6).

The individual values of all subjects will be listed. Listings will be sorted by treatment, subject number and visit (if visit is applicable in the respective listing). AE listings will be sorted by assigned treatment (see [Section 7.8.1](#) below for details). The listings will be contained in Appendix 16.2 (SDL) of the CTR.

The following standard descriptive statistical parameters will be displayed in summary tables of continuous variables:

N	number of non-missing observations
Mean	arithmetic mean
SD	standard deviation
Min	minimum
Median	median
Max	maximum

For serum concentrations as well as for all PK parameters the following descriptive statistics will additionally be calculated:

CV	arithmetic coefficient of variation
gMean	geometric mean
gCV	geometric coefficient of variation

For PK parameters the following descriptive statistics will additionally be calculated:

P10	10 th percentile
Q1	1 st quartile
Q3	3 rd quartile
P90	90 th percentile

The data format for descriptive statistics of serum concentrations will be identical with the data format of the respective concentrations. The descriptive statistics of PK parameters will be calculated using the individual values with the number of decimal places as provided by the evaluation program. Then the individual values as well as the descriptive statistics will be reported with three significant digits in the CTR.

Tabulations of frequencies for categorical data will include all possible categories and will display the number of observations in a category as well as the percentage (%) relative to the respective treatment group. Percentages will be rounded to one decimal place. The category missing will be displayed if and only if there actually are missing values. Percentages will be based on all subjects in the respective subject set whether they have non-missing values or not.

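### SAP 7.8.4 plans no listing or summary of ECG values, so QTc change from baseline appears in no planned output and ECG is reported only as investigator-judged findings

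*SAP*

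**What the plan says.** Protocol 2.2.2.2 and SAP 5.3.1 both name 12-lead ECG as a safety parameter, listed beside adverse events, laboratory tests and vital signs.

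SAP 7.8.4 keeps only part of it: "Abnormal findings will be reported as baseline conditions (at screening) or as AEs (during the trial) if judged clinically relevant by the investigator". It then closes the matter: "No separate listing or analysis of ECG data will be prepared".

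Elsewhere the plan reads differently. The footnote to SAP Table 6.1: 1 points to the definition of baseline, "which will be used in the statistical analyses of safety laboratory data, ECG and vital signs". Protocol 7.3.4 bases the safety analysis on the 2.2.2.2 assessments, gives continuous data descriptive statistics, and names ECG among the measurements to be assigned to treatments, with details left to the SAP. The same section also says that relevant ECG findings are reported as adverse events.

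Protocol 3.3.4.3, item 6, sets a numeric ECG criterion: "Further dosing will be stopped if at least 2 subjects at one group (14 subjects) have relevant individual QT prolongations", defined as "a QTc increase of greater than 60 ms from baseline in connection with absolute QT or QTc greater than 500 ms" and confirmed by a repeat recording. The protocol's abbreviation list defines QTc as corrected by Fridericia or Bazett and does not choose between them.

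**The concern.** Laboratory data and vital signs each get summaries over time, change from baseline and listings (SAP 7.8.2 and 7.8.3). ECG gets none of these, although a trial-level criterion in item 6 rests on its numeric values.

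Two things are at stake. A reader of the report could not see how close any subject came to the QTc limits. And in an open-label trial, the only filter between the recordings and the report is an investigator who knows the route given. Protocol 3.2 defends the open design on the ground that the endpoints come from a laboratory blinded to allocation; that defence does not reach a judgement about ECG relevance. Subcutaneous dosing is also new here, because the first-in-human trial was intravenous only.

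**Working it through.** No sample-size or error-rate figure in the plan bears on this point, so there is none to reproduce. The check is mainly a comparison of passages.

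**1. Which passages conflict with SAP 7.8.4**
- SAP Table 6.1: 1 footnote: real conflict. It presupposes a statistical analysis of ECG that 7.8.4 rules out.
- Protocol 7.3.4: conflict in part. It calls for a descriptive analysis of the 2.2.2.2 assessments. Its sentence on reporting relevant ECG findings as adverse events supports the first half of 7.8.4, but does not say that values go unlisted or unanalysed. SAP 4 nevertheless declares full agreement with the protocol.
- SAP 7, "The individual values of all subjects will be listed": weak. It is a general statement, and a specific section can override it.
- Protocol 5.2.4, "the repeated ECG will be used for analysis": weak. It says which recording counts after a quality repeat and promises no statistics.

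**2. Item 6 traced through the planned outputs**
- Needed: baseline QTc, on-treatment QTc, their difference, absolute QT or QTc, and the confirming repeat.
- Planned: adverse event tables and listings (7.8.1), laboratory data (7.8.2), blood pressure and pulse rate (7.8.3), local tolerability (7.8.5). None carries a QT or QTc value.
- Heart rate is covered: protocol 5.2.2 treats it as equal to pulse rate, and SAP 7.8.3 summarises pulse rate over time and as change from baseline.
- The criterion turns on 2 of 14 subjects in a group, or 14.3%, so single values matter.

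**3. How much data is affected**
- The IV flow chart shows 12 ECGs from 0:30 to 1320 h plus one at the end-of-trial visit, 13 post-dose per subject. 13 × 14 = 182 in that group.
- The SC chart's columns are too disturbed in the available text for a reliable count.

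**4. What a summary could show**
- The 90% CI half-width for a mean change in one group of 14 is t(0.95, 13) × SD/√14 = 1.771 × SD/3.742 = 0.473 × SD.
- The documents give no SD for QTc change. Assumed values of 10, 15 and 20 ms give 4.7, 7.1 and 9.5 ms.

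**5. Whether the correction formula matters**
- Bazett is QT/√RR; Fridericia is QT/RR^(1/3), with RR in seconds.
- At 100 bpm (RR 0.600), QT 390 ms gives 503 and 462 ms, on opposite sides of 500. But these are resting supine ECGs in subjects whose pulse at entry is 45 to 90 bpm.
- At 90 bpm (RR 0.667), the same QT gives 478 and 446 ms, both below 500.
- At 90 bpm, exceeding 500 ms needs QT above 500 × 0.8165 = 408 ms (Bazett) or 500 × 0.8736 = 437 ms (Fridericia). The formulas disagree on the absolute limit only for QT between those values.

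**The case against.** The strongest case on the other side is this. Item 6 is a conduct rule, applied while dosing is under way and confirmed by a repeat ECG. The recordings are read and stored electronically at the site (protocol 5.2.4), ECG results are named as source documents (8.3.1), and monitors, auditors and inspectors have direct access (8.3.2). No SAP table is needed to apply the rule or to document it. This stands. A reader might infer that the plan leaves no way to show whether the criterion was met; the documents do not support that. What is missing is its display in the report.

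A reader might also infer that the SAP discards ECG on its own initiative. That goes too far: protocol 7.3.4 and 5.2.4 both route clinically relevant ECG findings to adverse events, and those findings will be tabulated. Nor is a heart-rate shift hidden, given the pulse-rate summaries.

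The Table 6.1: 1 footnote may be an editorial slip, since the table title and the text below it name laboratory data and vital signs but not ECG. Even so, the two statements cannot both stand.

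Finally, this is a 28-subject exploratory trial of an antibody whose first-in-human trial reported no clinically relevant ECG changes, and without placebo a small mean shift could not be separated from time effects. That limits what the summaries could prove. It does not justify leaving a named, repeatedly measured safety parameter without any reported value.

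**Conclusion.** The point holds as a reporting gap with an internal contradiction. Under SAP 7.8.4 no QT or QTc value, change from baseline or count above a limit appears in any planned output. The item 6 criterion therefore cannot be verified from the report, and a common QTc shift below the level of an individual adverse event would not be seen. About 182 post-dose ECGs in the IV group are affected, assuming the flow chart marks were read correctly, plus those in the SC group.

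Summaries would locate a within-group mean change to roughly ±5 to ±10 ms if the SD lies between 10 and 20 ms, which is an assumption. They could not attribute it to the drug.

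The unchosen QTc correction is a secondary ambiguity. A reader might infer from a 100 bpm example that the two formulas readily give opposite answers on the criterion. At 90 bpm the same QT leaves both below 500 ms, so the case for naming a formula rests on clarity and not on that example.

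**What to change.** Replace the last sentence of SAP 7.8.4 with:
- a listing of ECG intervals, at least QT and QTc, by subject and time;
- descriptive statistics of values and of change from baseline (as defined in SAP 6.7), by route and planned time;
- counts of subjects by route above the limits the protocol already states: QTc increase above 60 ms, QT or QTc above 500 ms, and both together.

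State in the SAP which QTc correction these outputs use, at the sponsor's choice, or show both. The sponsor should reconcile that statement with the QTc wording in exclusion criterion 20 and protocol 3.3.4.3, and reconcile SAP 7.8.4 with the Table 6.1: 1 footnote and protocol 7.3.4. No threshold or clinical rule changes.

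The cost is one listing and two descriptive tables. The documents do not say that the intervals are held in the trial database; if they are not, they must be transferred from the single site, where the ECGs are stored electronically. Any rewording of the protocol itself would be a separate amendment, which the SAP outputs do not need to wait for. The results should be labelled descriptive, because both groups receive the same active dose and there is no placebo arm.
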